16.4.2 DAY 1,2,3

On each day, the following assessments should be completed. There should be at least 12 hours between each assessment. Assessments after Day 1 are omitted if the patient is discharged from ICU.

- Concomitant medications
- Clinical End-point Assessment includes: Survival (Y/N), On mechanical ventilation (Y/N), In ICU (Y/N), In Hospital (Y/N), Use of anti-coagulation (drug, dose, intent: prophylaxis vs therapeutic), WHO Ordinal Score (See Appendix D for scale). If patient is in ICU then the following assessment will be completed: Sequential Organ Failure Assessment (SOFA, See [Appendix B](#) for template form), PaO₂/FiO₂, following ventilation parameters (as applicable): type of ventilation (CPAP, BiPAP, or intubation)/ ventilation rate/ pulse/ tidal volume/ positive end-expiratory pressure (PEEP), recording of vasoactive drugs and renal support, recording of supportive interventions that can impact clinical end-points (use of prone ventilation, use of paralytics, use of pulmonary vasodilators, use of corticosteroids, use of oral decontamination and raising the head of the patient to at least 30° to prevent ventilator-associated pneumonia).
- Research blood collection: All protocol required research blood collection assessments must be conducted in accordance with Laboratory Manual.
- Exploratory Bronchoalveolar lavage: **This should be done only once during this period.** There should be at least 48h passed since the collection for Screening Visit (Section 16.4.1). If BAL can not be performed, then tracheal aspirate.
- CBC with differential: Only if performed as Standard of Care.
- Serum chemistry: Only if performed as Standard of Care. Chemistry includes: Glucose, Ca, Mg, Phos, ALP, Albumin, Total Protein, Total Bilirubin, K, Na, Cl, HCO₃, BUN, Cr, ALT, AST, LDH, Amylase.
- CRP, ferritin, D-Dimer.
- PT/INR, PTT: If performed as Standard of Care.

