- Urinalysis: Samples should be taken in the morning between 04:00 and 10:00 using the values closest to 10:00. (mandatory for Arm 1, only if done as part of standard of care at institution for Arm 2)
- ECG: Electrocardiogram may be performed as standard of care, at the discretion of the Investigator.
- Research blood collection: All protocol required research blood collection assessments must be conducted in accordance with Laboratory Manual.
- Chest Imaging: CT scan or Chest X-Ray (Once before first infusion and once between Days 1-6)
- AE review and evaluation
- PT/INR, PTT (mandatory for both Arms)

After completion of Descartes-30 infusion:

1. On Day(s) 0 and 2, Research Blood Collection at 30min (± 10 min). Please See Laboratory Manual for more details.
2. On Day(s) 0 and 2, PT/INR, PTT at 30min (± 10 min).
3. For details of post-infusion clinical monitoring for 4 hours (Arm 1) or 1 hour (Arm 2) after completing infusion, please see Section 7.1.2.3.

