- Urinalysis: Samples should be taken in the morning between 04:00 and 10:00 using the values closest to 10:00. (mandatory for Arm 1, only if done as part of standard of care for Arm 2)
- Research blood collection: At least once between Day 3 and Day 6. All protocol required research blood collection assessments must be conducted in accordance with Laboratory Manual.
- Exploratory Bronchoalveolar lavage: **Should be done at least once during this period if it was performed prior to administration of cells.** If BAL is not performed then tracheal aspirate or sputum (induced or expectorated).
- Chest Imaging: CT scan or Chest X-Ray. Once between Days 1-6.
- AE review and evaluation
- PT/INR, PTT (Should be done at least once during this period, for patients in both Arms).

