7.2.2.3 THROMBOEMBOLIC EVENTS

Recent pre-clinical and clinical data demonstrate that MSCs can express or increase secretion of proteins associated with coagulation signals.^{49,50} However, these incident events are rare (17 events in 1112 patients in the meta-analysis³⁹), and were reported in both treatment and control groups with no significant difference associated with administration of MSCs. Thus, these events will likely be rare and as such investigators should evaluate embolic events in their differential diagnosis while managing clinical changes within 24 hours following Descartes-30 infusion.

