16.3 SCHEDULE OF ACTIVITIES

Procedures	Study Visit 1/ Screening Visit ^j	Study Visit 2/ Day 1	Study Visit 3/ Day 2	Study Visit 4/ Day 3	Study Visit 5/ Day 4-6 ^f	Study Visit 6/ Day 28 ^g
Informed consent	X					
Demographics	X					
Medical history	X					
Concomitant Medications	X	X	X	X	X	X
Clinical End-point Assessment ^a		X	X	X	X	X
Research Blood Collection ^b	X	X	X	X	X ^e	X ^f
Exploratory BAL ^c	X				X ^e	
APACHE II score ^d	X					
CBC with differential ^h	X	X	X	X	X ^e	
Serum chemistry ^{h,i}	X	X	X	X	X ^e	
CRP, ferritin, D-Dimer	X	X	X	X	X ^e	
PT/INR, PTT ^h	X	X	X	X	X ^e	
Chest X-Ray or CT Scan	X				X ^e	X

a Clinical End-Point Assessments include: Survival (Y/N), On mechanical ventilation (Y/N), In ICU (Y/N), In Hospital (Y/N), Use of anti-coagulation (drug, dose, intent: prophylaxis vs therapeutic), WHO Ordinal Score. If patient is in ICU then the following assessment will be completed: Sequential Organ Failure Assessment (SOFA), PaO₂/FiO₂, ventilation variables (See Section 6 for details), recording of vasoactive drugs and renal support, recording of supportive interventions that can impact clinical end-points (i.e., use of prone ventilation, use of paralytics, use of pulmonary vasodilators, use of corticosteroids, use of oral decontamination and raising the head of the patient to at least 30° to prevent ventilator-associated pneumonia)

b See Laboratory Manual for details of sample collection for exploratory assays.

c If not possible, use tracheal aspirates.

d See [Appendix A](#) for APACHE II score system.

e To be done only once during this period

f If still in ICU

g Day 28 or last day of hospital, whichever comes first.

h If performed as Standard of Care

i Serum Chemistry includes Glucose, Ca, Mg, Phos, ALP, Albumin, Total Protein, Total Bilirubin, K, Na, Cl, HCO₃, BUN, Cr, ALT, AST, LDH, Amylase

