16.4.3 DAYS 4-6

If the patient is still in ICU, the following assessments should be completed. There should be at least 12 hours between each assessment.

- Concomitant medications: Should be done daily.
- Clinical End-point Should be done daily. Assessment includes: Survival (Y/N), On mechanical ventilation (Y/N), In ICU (Y/N), In Hospital (Y/N), Use of anti-coagulation (drug, dose, intent: prophylaxis vs therapeutic), WHO Ordinal Score (See Appendix D for scale). If patient is in ICU then the following assessment will be completed: Sequential Organ Failure Assessment (SOFA), PaO₂/FiO₂, following ventilation parameters (as applicable): type of ventilation (CPAP, BiPAP, or intubation)/ ventilation rate/ pulse/ tidal volume/ positive end-expiratory pressure (PEEP), recording of vasoactive drugs and renal support, recording of supportive interventions that can impact clinical end-points (use of prone ventilation, use of paralytics, use of pulmonary vasodilators, use of corticosteroids, use of oral decontamination and raising the head of the patient to at least 30° to prevent ventilator-associated pneumonia)
- Research blood collection: Only once during this period. All protocol required research blood collection assessments must be conducted in accordance with Laboratory Manual.

- Exploratory Bronchoalveolar lavage: **This should be done only once during this period if not done on Days 1-3.** If BAL can not be performed, then tracheal aspirate.
- CBC with differential: Only once during this period and if performed as Standard of Care.
- Serum chemistry: Only once during this period and if performed as Standard of Care. Chemistry includes: Glucose, Ca, Mg, Phos, ALP, Albumin, Total Protein, Total Bilirubin, K, Na, Cl, HCO₃, BUN, Cr, ALT, AST, LDH, Amylase.
- CRP, ferritin, D-Dimer: Only once during this period.
- PT/INR, PTT: Only once and if performed as Standard of Care.
- Chest Imaging: CT scan (preferred) or Chest X-Ray, if performed as standard of care once during this period.

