16.5 BIOMARKER ANALYSIS AND STATISTICAL CONSIDERATIONS

16.5.1 SAMPLE SIZE

Given the small study size, statistical analyses will be primarily descriptive. Results of Descartes-30 treated patients will be compared to the parallel control patients (one-sided Student's t-test for all continuous variables). Longitudinal analysis of pharmacokinetics and pharmacodynamics biomarkers and will be used to inform (1) additional cohort expansion and/or (2) statistical and power considerations for randomized trial design and inferential statistics.

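### PT/INR and PTT are required in treated patients but taken in Appendix E controls only when clinically ordered, which can bias the treated-versus-control comparison of these two tests

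*Combined protocol and SAP*

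**What the plan says.** **Treated patients.** Section 6.2 lists, among the assessments before each infusion, "PT/INR, PTT (mandatory for both Arms"), and after infusion "On Day(s) 0 and 2, PT/INR, PTT at 30min". Section 6.3 adds "PT/INR, PTT (Should be done at least once during this period, for patients in both Arms"), within a section that applies only while the patient remains in the administering unit. The main schedule in Section 1 agrees.

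**Controls (Appendix E).** Sections 16.4.1 and 16.4.2 (Screening, Days 1-3) say "PT/INR, PTT: If performed as Standard of Care". Section 16.4.3 (Days 4-6) says "PT/INR, PTT: Only once and if performed as Standard of Care". The PT/INR, PTT row in Section 16.3 carries the footnote "h If performed as Standard of Care", so table and text agree and this is not a slip. CRP, ferritin and D-dimer carry no such condition, and research blood is drawn from controls at the same visits.

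**Analysis.** Section 16.5.1 calls the analyses primarily descriptive, then compares treated with parallel control patients by "one-sided Student's t-test for all continuous variables". It gives no direction, no significance level and no rule for control values that exist only because a clinician ordered the test. Sections 16.5.2 and 16.5.3 are redacted.

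**The concern.** One variable has two collection rules, and the analysis section then compares the groups on it. INR and PTT are continuous, so they fall within the Section 16.5.1 test as worded. A control has a value only if someone ordered one. Where ordering is selective, the likely triggers are anticoagulation, bleeding or known coagulopathy, all of which go with longer times. The tested controls then overstate the control mean.

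The consequence depends on the direction of any drug effect. A true prolongation in treated patients is partly or wholly cancelled. No effect, or a true shortening, looks like a larger shortening than it is.

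The sponsor evidently values the test. In Arm 2, CBC, chemistry and urinalysis on infusion days and Days 3-6 drop to standard of care, while PT/INR and PTT stay mandatory. Section 7.2.2.3 reports that "MSCs can express or increase secretion of proteins associated with coagulation signals". The main study has no control arm, so these controls are the only concurrent untreated reference in the readable text.

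**Working it through.** The plan states no control number, power or significance level (Section 9.1 says no formal calculation was made), so there is no figure to reproduce. The check compares the collection rules and then sizes the bias under stated assumptions.

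**1. The rules side by side**

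| Period | Treated, both arms | Controls |
|---|---|---|
| Before treatment | Day 0, before infusion: mandatory (6.2) | Screening: standard of care only (16.4.1) |
| Infusion days / Days 1-3 | Before each infusion, plus 30 min after on Days 0 and 2 (6.2) | Standard of care only (16.4.2) |
| Days 3-6 / Days 4-6 | At least once, if in the administering unit (6.3) | Once, standard of care only (16.4.3) |

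**2. Size of the bias in the control mean**

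Assumed, not from the documents: INR log-normal, median 1.2, log SD 0.2, the same in both groups; a control in the top third of INR is tested with probability 0.9, any other with probability 0.4.

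- Mean INR: 1.2 × exp(0.2²/2) = 1.224.
- Mean in the top third: 3 × 1.224 × Φ(0.2 − 0.431) = 1.501.
- Mean in the lower two thirds: (1.224 − 1.501/3) × 3/2 = 1.086.
- Share of controls tested: (0.9 + 2 × 0.4)/3 = 0.57.
- Mean among tested controls: (0.9 × 1.501 + 0.8 × 1.086)/1.7 = 1.306.
- Bias: 1.306 − 1.224 = +0.08. A true rise of 0.15 in treated patients would appear as about 0.07.

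With milder selection (0.8 versus 0.5): (0.8 × 1.501 + 1.0 × 1.086)/1.8 = 1.270, a bias of about +0.05.

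**3. Effect on the test**

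Simulated pooled-variance t-test, one-sided 5% (assumed), 24 treated ARDS patients (12 in Arm 1 plus 12 in the ARDS expansion cohort, Section 4.2), 12 or 24 controls (assumed). Each cell gives the result for 12 / 24 controls; ranges are the spread between repeat runs. The two result columns are alternatives: a one-sided test looks in one direction, and Section 16.5.1 does not say which.

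| Control testing | Test directed at prolongation: power for a true +0.15 | Test directed at lower values: false-positive rate with no effect |
|---|---|---|
| All controls tested | 52-53% / 66-67% | 5% / 5% |
| 0.9 versus 0.4 | 15% / 20% | 19% / 24-25% |
| 0.8 versus 0.5 | 24-25% / 34% | 12% / 13-14% |

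Part of the power loss is simply fewer values. Testing the same share of controls (about 57%) at random gives 39-41% / 54-56%. The further fall to 15% / 20% is bias.

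**4. Second model**

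If a share q of controls is tested, and the tendency to be tested correlates ρ with the true value, the control mean shifts by ρ·φ(z₁₋q)/q in SD units:

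- q = 0.8, ρ = 0.3: 0.3 × 0.280/0.8 = 0.11 SD.
- q = 0.6, ρ = 0.5: 0.32 SD.
- q = 0.4, ρ = 0.8: 0.77 SD.
- ρ = 0, any q: no bias, only lost precision.

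With 12 controls, a true prolongation of 0.5 SD is then estimated as 0.39, 0.18 or −0.27 SD in the first three cases, with power 0.27, 0.10 or 0.004, against 0.40 with all controls tested. The result depends wholly on q and ρ, which the documents do not give.

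**The case against.** The strongest reply has five parts.

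- **The comparison is inferred.** No readable sentence names a PT/INR or PTT comparison, and Section 16.5.1 calls its analyses primarily descriptive. Sections 16.5.2-16.5.3 are redacted and the opening text of Appendix E was not available for this check, so a narrower variable list may exist. This stands as a limit. The readable wording nonetheless covers all continuous variables.
- **Selection is assumed.** Controls are assessed after Day 1 only while in ICU. If the ICU runs coagulation tests on everyone, the bias is near zero. This stands, but the plan neither requires nor records routine testing.
- **The cited risk points the other way.** A reader might infer that the design hides coagulation harm in general. Section 7.2.2.3 concerns thromboembolic events, and inflated control values would exaggerate a shortening, not hide it. Only a prolongation can be masked. D-dimer is required in both groups.
- **Safety monitoring does not use controls.** A reader might also infer that patient safety oversight is weakened. The DLT definition (8.1.2) and pausing rules (8.5) make no reference to controls, laboratory safety is tabulated descriptively (9.2), and treated patients have their own pre- and post-infusion values.
- **Treated sampling is not unconditional.** Infusion-day samples belong to infusions given after a stability check (7.1.2.1), and the Days 3-6 sample applies only in the administering unit. This stands.

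Anticoagulant use is recorded in both groups, so one likely trigger can be examined. That helps interpretation, but it does not recover values for untested controls.

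**Conclusion.** The point holds in a limited form. The difference in collection rules is certain from the text. The bias is conditional: upward in control PT/INR and PTT if testing is selective, near zero if it is routine. Under the assumed selection the bias is about 0.05 to 0.08 INR. That is enough to cut power for a rise of 0.15 from about 52% to between 15% and 25% with 12 controls, and from about 66% to between 20% and 34% with 24. If the test is directed at lower values instead, the 5% false-positive rate becomes 12% to 25%. The INR distribution, testing probabilities, control number, significance level and direction are all assumptions.

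The documents do not support a claim that coagulation harm as a whole would go unseen or that the trial's safety rules are compromised. The defect is confined to the treated-versus-control comparison of these two tests. It merits correction because Section 16.5.1 sets up that comparison and the remedy is cheap.

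**What to change.** **Preferred.** Remove footnote h from the PT/INR, PTT row in Section 16.3 and the standard-of-care condition for these tests in Sections 16.4.1-16.4.3. Run the assay at the research blood draws already scheduled for controls (Screening, Days 1-3, once on Days 4-6). Cost: one extra tube and a routine assay at each of those draws. Treatment is unchanged.

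**Otherwise.** State in Section 16.5.1 that PT/INR and PTT are excluded from the treated-versus-control test because controls are tested at clinical discretion. Report them descriptively, with the number of controls tested at each visit and by anticoagulant use. Cost: a sentence or two and one table; the concurrent comparison for these tests is given up.

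If the redacted sections already exclude PT/INR and PTT, a cross-reference in Section 16.5.1 is enough.

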16.4.3 DAYS 4-6

If the patient is still in ICU, the following assessments should be completed. There should be at least 12 hours between each assessment.

- Concomitant medications: Should be done daily.
- Clinical End-point Should be done daily. Assessment includes: Survival (Y/N), On mechanical ventilation (Y/N), In ICU (Y/N), In Hospital (Y/N), Use of anti-coagulation (drug, dose, intent: prophylaxis vs therapeutic), WHO Ordinal Score (See Appendix D for scale). If patient is in ICU then the following assessment will be completed: Sequential Organ Failure Assessment (SOFA), PaO₂/FiO₂, following ventilation parameters (as applicable): type of ventilation (CPAP, BiPAP, or intubation)/ ventilation rate/ pulse/ tidal volume/ positive end-expiratory pressure (PEEP), recording of vasoactive drugs and renal support, recording of supportive interventions that can impact clinical end-points (use of prone ventilation, use of paralytics, use of pulmonary vasodilators, use of corticosteroids, use of oral decontamination and raising the head of the patient to at least 30° to prevent ventilator-associated pneumonia)
- Research blood collection: Only once during this period. All protocol required research blood collection assessments must be conducted in accordance with Laboratory Manual.

- Exploratory Bronchoalveolar lavage: **This should be done only once during this period if not done on Days 1-3.** If BAL can not be performed, then tracheal aspirate.
- CBC with differential: Only once during this period and if performed as Standard of Care.
- Serum chemistry: Only once during this period and if performed as Standard of Care. Chemistry includes: Glucose, Ca, Mg, Phos, ALP, Albumin, Total Protein, Total Bilirubin, K, Na, Cl, HCO₃, BUN, Cr, ALT, AST, LDH, Amylase.
- CRP, ferritin, D-Dimer: Only once during this period.
- PT/INR, PTT: Only once and if performed as Standard of Care.
- Chest Imaging: CT scan (preferred) or Chest X-Ray, if performed as standard of care once during this period.

16.4.4 DAY 28 (OR DAY OF DISCHARGE)

These assessments will be done on the day the patient leaves the hospital or on Day 28, whichever comes earlier.

- Concomitant medications
- Clinical End-point Assessment includes: Survival (Y/N), On mechanical ventilation (Y/N), In ICU (Y/N), In Hospital (Y/N), Use of anti-coagulation (drug, dose, intent: prophylaxis vs therapeutic), WHO Ordinal Score. If patient is in ICU then the following assessment will be completed: Sequential Organ Failure Assessment (SOFA), PaO₂/FiO₂, ventilation variables [type of ventilation (CPAP, BiPAP, or intubation), ventilation rate, pulse, tidal volume, positive end-expiratory pressure (PEEP)], recording of vasoactive drugs and renal support, recording of supportive interventions that can impact clinical end-points (use of prone ventilation, use of paralytics, use of pulmonary vasodilators, use of corticosteroids, use of oral decontamination and raising the head of the patient to at least 30° to prevent ventilator-associated pneumonia).
- Chest Imaging: CT scan (preferred) or Chest X-Ray.

16.5 BIOMARKER ANALYSIS AND STATISTICAL CONSIDERATIONS

16.5.1 SAMPLE SIZE

Given the small study size, statistical analyses will be primarily descriptive. Results of Descartes-30 treated patients will be compared to the parallel control patients (one-sided Student's t-test for all continuous variables). Longitudinal analysis of pharmacokinetics and pharmacodynamics biomarkers and will be used to inform (1) additional cohort expansion and/or (2) statistical and power considerations for randomized trial design and inferential statistics.

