5.3 SCREEN FAILURES

[figure not shown]
Screen failures are defined as subjects who consent to participate in the clinical study but never receive Descartes-30 cells. A minimal set of screen failure information is required including demography and screen failure details. Screen failure data will not be recorded within the Case Report Form (CRF).

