7.1.2 DOSING AND ADMINISTRATION

7.1.2.1 PRE-INFUSION MONITORING AND DELAY OF CELL INFUSION

[figure not shown]
Infusions can be delayed up to 96 hours based on PI discretion. Prior to all Descartes-30 infusions, patients should be observed for 2 hours (\pm 30 min) to document their stability by meeting the following parameters and based on PI's best clinical judgement:

1. Patient is not requiring a change in ventilator settings
2. Stable use of vasopressors if the patient required vasopressors for blood pressure support.
Stable use is defined as increasing no more than 50% of baseline recorded at initiation of monitoring.

During 2-hour monitoring, following parameters should be recorded at least every 30 min: ventilation variables [type of ventilation (CPAP, BiPAP, or intubation), ventilation rate, pulse, tidal volume, positive end-expiratory pressure (PEEP)], recording of vasoactive drugs and renal support and vital signs [include core temperature, mean arterial pressure (mmHg), pulse (beats/min), respiratory rate (breaths/min)]. If patients do not meet stability criteria for 2 hours, infusion can be delayed for up to 96 hours. If infusion is delayed, the patient will be periodically monitored to assess stability. If infusion is delayed more than 96 hours due to medical instability, patients will come off study treatment. Infusions can also be delayed up to 96 hours in case of a holiday or by PI's discretion.

Patients experiencing toxicities that are probably or definitely related to Descartes-30 will have their next Descartes-30 dose delayed until these toxicities have resolved to at least Grade 2, unless in the documented opinion of the site Principal Investigator and the medical monitor it is reasonable to proceed. During this period, patients will be assessed to record adverse events and decide whether the patient meets criteria for cell infusion. The discussions between the Medical Monitor and site Principal Investigator will be documented. If a dose is delayed for more than 96 hours, the patient will come off study treatment.

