16.2 OVERALL STUDY DESIGN

This is a biospecimen and clinical data collection protocol in patients diagnosed with ARDS.

The design of the study stems from the treatment schedule described in the DC30-1A protocol.

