16.4.1 SCREENING

All inclusion and exclusion criteria will be reviewed by the Investigator or qualified designee at the Screening Visit to ensure that the subject qualifies for the study. All inclusion criteria must be met, and none of the exclusion criteria may apply. Subjects found ineligible during the review of inclusion/exclusion will not proceed through the remaining screening process.

- Informed consent
- Demographics, Medical History
- Concomitant medications
- Research blood collection: All protocol required research blood collection assessments must be conducted in accordance with the Laboratory Manual and the Schedule of Activities. Laboratory requisition forms must be completed, and samples must be clearly labeled with the subject number, protocol number, site number, and visit date. Details for the preparation and shipment of samples will be provided by the laboratory and are detailed in the Laboratory Manual.
- Exploratory Bronchoalveolar lavage: See Laboratory Manual for more details. Should be done per 'institute's standards of operations. If BAL can not be performed then tracheal aspirate.
- Clinical End-point Assessment includes: Survival (Y/N), On mechanical ventilation (Y/N), In ICU (Y/N), In Hospital (Y/N), Use of anti-coagulation (drug, dose, intent: prophylaxis vs therapeutic), WHO Ordinal Score (See Appendix D for scale). If patient is in ICU then the following assessment will be completed: Sequential Organ Failure Assessment (SOFA, See [Appendix B](#) for template form), PaO₂/FiO₂, following ventilation parameters (as applicable): type of ventilation (CPAP, BiPAP, or intubation)/ ventilation rate/ pulse/ tidal volume/ positive end-expiratory pressure (PEEP), recording of vasoactive drugs and renal support, recording of supportive interventions that can impact clinical end-points (use of prone ventilation, use of paralytics, use of pulmonary vasodilators, use of corticosteroids, use of oral decontamination and raising the head of the patient to at least 30° to prevent ventilator-associated pneumonia).
- CBC with differential: Only if performed as Standard of Care.
- Serum chemistry: Only if performed as Standard of Care. Chemistry includes: Glucose, Ca, Mg, Phos, ALP, Albumin, Total Protein, Total Bilirubin, K, Na, Cl, HCO₃, BUN, Cr, ALT, AST, LDH, Amylase.
- CRP, ferritin, D-Dimer:
- PT/INR, PTT: If performed as Standard of Care.
- Chest Imaging: CT scan (preferred) or Chest X-Ray.

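### On the readable text, Section 16.5.1 compares treated patients with non-randomised ARDS controls by a one-sided t-test with no baseline adjustment, so a baseline difference could mimic or mask a drug effect

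*Combined protocol and SAP*

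**What the plan says.** Section 16.5.1 calls the analyses primarily descriptive because the study is small, then names one method: "Results of Descartes-30 treated patients will be compared to the parallel control patients (one-sided Student's t-test for all continuous variables". It gives no direction, significance level, covariate or control number. Its next sentence says that longitudinal biomarker analysis will inform cohort expansion and "statistical and power considerations for randomized trial design and inferential statistics".

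Section 16.2 describes the appendix: "This is a biospecimen and clinical data collection protocol in patients diagnosed with ARDS". No readable section says that these patients are the parallel controls; that is inferred from their sharing the appendix. Nothing readable describes random allocation or matching. The main study is open-label (4.2), and Arm 1 patients take the next slot in the active dose level (4.4).

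Some rules differ between the groups:

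- **Before dosing.** Section 7.1.2.1: "Prior to all Descartes-30 infusions, patients should be observed for 2 hours". No counterpart is readable for controls, whose screening section says only "All inclusion criteria must be met, and none of the exclusion criteria may apply".
- **Never dosed.** Consented patients who receive no cells are screen failures kept outside the CRF (5.3): "A minimal set of screen failure information is required including demography and screen failure details".
- **ICU discharge.** For controls (16.4.2): "Assessments after Day 1 are omitted if the patient is discharged from ICU". Section 6.2 sets no such condition for treated patients on Days 1 and 2.

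Section 16.3 schedules the "APACHE II score" at control screening, and the main schedule does so for treated patients.

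**The concern.** A two-sample t-test attributes any difference in means to group membership. Without randomisation, group membership also carries whatever separated the two sets of patients at entry. If one group is less ill at baseline, its markers differ with no drug effect; if it is more ill, a real effect may vanish.

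The one-sided form adds a separate limit: a shift opposite to the chosen direction, however large, is not flagged.

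This is the only treated-versus-control comparison readable in the plan. At stake is how the biomarker and clinical comparison is read, and what might be carried from it into later design work. The MTD is not affected.

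**Working it through.** The plan gives no alpha, control number, effect size or SD for this comparison, so there is no figure to reproduce. What follows is illustrative.

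**Inputs.** From the documents: 12 ARDS patients in Arm 1 and 12 in the Arm 2 ARDS Cohort, so 12 or 24 treated. Assumed: 12 controls; one-sided alpha 0.05; a never-dosed share of 10% or 20%, all from the sick end; marker-severity correlation 0.5; own-baseline correlation 0.5 or 0.7; APACHE II-severity correlation 0.7.

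**1. Shift in the treated mean.** If the worst fraction p of a standard normal severity is removed, the mean moves by φ(z)/(1 − p) SD.

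- p = 10%: 0.1755/0.9 = 0.195 SD
- p = 20%: 0.280/0.8 = 0.350 SD
- With marker-severity correlation 0.5: 0.0975 and 0.175 SD

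**2. False positives with no drug effect.** The rejection probability is P(T > t₀.₉₅), where T is noncentral t with n₁ + n₂ − 2 degrees of freedom and noncentrality d/√(1/n₁ + 1/n₂), that is 2.449d for 12 v 12 and 2.828d for 24 v 12.

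| Shift d (SD) | 12 v 12 | 24 v 12 |
|---|---|---|
| 0.0975 | 7.9% | 8.5% |
| 0.175 | 10.9% | 12.3% |
| 0.195 | 11.9% | 13.5% |
| 0.35 | 20.8% | 25.0% |

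The last two rows are the extreme case in which the marker is severity itself. At one-sided 0.025 the first two rows become 4.2-4.5% and 6.1-7.0%.

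**3. Masking.** A true 0.8 SD benefit is detected in 60.0% (12 v 12) or 71.7% (24 v 12) of trials with no imbalance. An unfavourable gap of 0.195 SD leaves a net 0.605 SD: 41.7% or 51.3%. A gap of 0.35 SD leaves 0.45 SD: 28.2% or 34.6%.

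**4. Untested direction.** A true 0.8 SD shift the other way is flagged by the one-sided test in at most 0.02% of trials. A two-sided 95% interval excludes zero in 46.6% or 59.4%.

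**5. What adjustment achieves.** Simulation of the never-dosed mechanism, 8,000 runs per setting (Monte Carlo SE about 0.003), marker-severity correlation 0.5, no drug effect:

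| Analysis | Rejection rate |
|---|---|
| One-sided 0.05, unadjusted | 7.5-13.2% |
| One-sided 0.05, own baseline | 6.0-8.8% |
| One-sided 0.05, own baseline and APACHE II | 5.6-7.2% |
| Two-sided 95% interval, both covariates | 4.8-5.8% |

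Repeat runs agree: about 8-14% unadjusted and 5-8% with both covariates.

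**6. Are the baselines collected?** SOFA, PaO2/FiO2, CRP, ferritin, D-dimer and research blood are scheduled before infusion on treated Day 0 (Sections 1 and 6.2) and on control Day 1 (16.3 and 16.4.2), before the ICU-discharge rule applies. SOFA and PaO2/FiO2 are ICU-only in both groups. APACHE II is scheduled at screening in both.

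**The case against.** **Redaction.** Section 16.5.3, where markers and models would be defined, is redacted, as is most of 16.5.2, and the opening of Appendix E is not in the available text. A reader might infer that the plan contains no adjustment at all. The documents do not support that; the point is confined to what can be read. The results compared may also be change scores, since Section 9.3 lists change for SOFA and PaO2/FiO2. Section 16.5.1 does not say.

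**Decision link.** A reader might infer that this t-test decides cohort expansion or the later trial. Section 16.5.1 ties those to longitudinal biomarker analysis, in a separate sentence from the test. The link is possible but not stated.

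**Selection.** A reader might infer that the stability check removes the sickest patients and so favours the drug. It is not a severity cut: it looks for changing ventilator settings and rising vasopressor use, allows up to 96 hours of delay and leaves room for judgement. The 10-20% truncation illustrates a mechanism and is not an estimate. The ICU-discharge difference is also narrow: two days, mainly blood markers and the ordinal score.

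**Sidedness.** A reader might infer that harm would go unseen. It would not: DLTs, adverse events and descriptive laboratory tables (8.1.2, 9.2) are separate.

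**Pneumonia patients.** Read literally, treated patients include the PNA Cohort, but 16.5.1 does not say that they enter a comparison with ARDS controls.

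What stands is that a specific test is named, it is one-sided, the readable text neither randomises nor adjusts, and baseline data that could be used are already scheduled in both groups.

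**Conclusion.** The concern holds on the readable text and in limited form. The one comparison named is an unadjusted one-sided t-test against controls for whom no randomisation is described, so a baseline gap could produce or conceal an apparent effect. The direction and size of any gap in this trial are unknown. The figures of about 8-13% unadjusted against 6-7% adjusted rest on an assumed alpha, control number, never-dosed share and correlations; they show that a modest gap matters, not how large it is here. For a fixed gap, more patients raise the false-positive rate (compare 12 v 12 with 24 v 12).

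The comparison is exploratory. Because the plan itself calls these analyses primarily descriptive, adjusted estimates with two-sided intervals suit it better than one-sided tests. Confidence is medium because of the redactions.

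**What to change.** Replace the parenthesis in Section 16.5.1 with text such as:

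> Treated ARDS patients will be compared with ARDS controls; the PNA Cohort is summarised separately. The comparison is non-randomised and exploratory. Results are estimates with two-sided 95% confidence intervals, adjusted for the variable's own baseline where one exists and for APACHE II where available; outcomes with no own baseline (e.g. ventilator-free, ICU-free or hospital days) are adjusted for APACHE II only. Baseline is the last value before first infusion in treated patients and the Day 1 value in controls (for BAL or tracheal aspirate, the pre-infusion sample and the screening sample). Post-baseline values are compared at the closest matching elapsed time, keeping all collected time points including Day 28; BAL or tracheal aspirate is compared as one post-baseline sample with its elapsed time reported. The number contributing at each time point and the number consented but never dosed are reported. Any p-values are two-sided.

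If the redacted sections already specify adjustment or matching, 16.5.1 should refer to it.

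**Costs.** A few sentences and some programming; no new visits.

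- *Width.* A two-sided 95% half-width is 20-21% wider than a one-sided 95% bound. With two covariates (APACHE II assumed to add no precision), the net is 8-11% wider at own-baseline correlation 0.5, or 9-11% narrower at 0.7.
- *Residual confounding.* Adjustment handles only measured factors.
- *Missing baselines.* Control CBC, chemistry, PT/INR and PTT are standard-of-care only. Treated CRP, ferritin and D-dimer have no screening value, so Day 0 before infusion is their baseline and cannot also be an outcome.

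**Separate inconsistency to reconcile.** Section 16.3 schedules APACHE II at control screening but 16.4.1 omits it; 16.4.1 lists the clinical end-point assessment at screening but 16.3 does not schedule it there. Aligning them helps ensure that APACHE II is collected. Using control Day 1 as baseline avoids depending on the second mismatch.
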